8.4.2 Diary Data Visit Windows

The daily electronic diary entries reported during the Treatment Period will be classified into 8 weeks as follows:

Day 1-7 = Week 1
Day 8-14 = Week 2
Day 15-21 = Week 3
Day 22-28 = Week 4
Day 29-35 = Week 5
Day 36-42 = Week 6
Day 43-49 = Week 7
Day 50-56 = Week 8

Non-diary data, such as vital signs, clinical laboratory assessments, and ECGs, will be displayed and analyzed according to the nominal visit date on the eCRF. Assessments taken outside of protocol allowable windows for nominal visits will be displayed according to the slotting scheme presented in the SAP for unscheduled or out-of-window visits.

8.4.3 Baseline Definition

For each safety parameter, the most recent valid assessment recorded before randomization will be used as the baseline for all analyses of that safety parameter.

For efficacy parameters, the baseline values will be derived from data collected in the 2-week electronic diary assessment at the end of the Screening Period (baseline). The last 14 days of diary entries prior to Day 1 will be the default standard for derivation of these values.

The baseline SBM (CSBM) weekly rate will be the weekly average number of SBMs (CSBMs) recorded during the 2-week baseline assessment period. Baseline stool consistency, severity of straining during a BM, and abdominal symptoms will be calculated as follows: for each week of the baseline assessment, the weekly average is the sum of the non-missing scores recorded during the week divided by the total number of non-missing scores recorded during that week; the baseline is then equal to one-half of the sum of the two weekly average scores..

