9. The patient has clinical or laboratory signs and symptoms of significant cerebral, respiratory, renal, hepatobiliary, pancreatic, intestinal (including acute appendicitis, inflammatory bowel disease, or undiagnosed abdominal pain), endocrinologic, or infectious disease that in the investigator's judgment could interfere with study assessments or completion of the study. (Note: A patient with a history of thyroid disease may be enrolled if he or she has normal T3 and T4 at Screening. If the patient is taking medication for active thyroid disease, his or her T3 and T4 level must be within normal limits and the dose of any medication used to treat it must be stable for at least 30 days prior to Screening.)
10. The patient has any other medical condition or is receiving concomitant medication or therapy that would in the investigator's opinion compromise his or her safety or compliance with the study protocol or compromise data collection.
11. The patient has a history or evidence of drug or alcohol abuse in the 12 months before Screening.
12. The patient has a hypersensitivity, allergy, or contraindication to plecanatide.
13. The patient has received any experimental drug, including linaclotide and lubiprostone, or experimental therapy within 30 days of study start.
14. The patient is unable to tolerate protocol-prescribed rescue medication (Dulcolax®), or unwilling to use it as the only laxative for the duration of the trial.
15. The patient has taken a protocol-prohibited medication prior to randomization.
16. The patient and his or her parent/guardian are unable to communicate well with the study staff and comply with the study requirements (restrictions, appointments, and examination schedule). (The patient must be able to complete all required Daily BM and Symptom electronic diary entries during the Screening/Baseline period and for the duration of the study. The patient must also agree to receive a reminder daily via phone should he or she not complete the daily electronic diary entries.)

Exclusion Criteria Based on Baseline Diary Entries

17. Completion of < 5 of the 7 required daily diary entries in each week of the 2-week baseline diary assessment.
18. Use of rescue medication (Dulcolax®, bisacodyl) for more than 2 days during either of the two weeks of the 2-week baseline diary assessment.
19. ≥ 3 SBM per week for either week of the 2-week baseline diary assessment.

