5.2.2 Visit 2: Randomization / Day 1 of Treatment Period

Study eligibility must be confirmed ***prior to randomization***, including the following:

- Confirm that patient has used only study-supplied rescue medication laxative (Dulcolax[®]) since Visit 1
- Urine drug screen (see **Section 4.3.2** for details)
- Urine pregnancy test, if applicable
- Update medical history and concomitant medications, as necessary

The last 14 days of daily diary entries prior to randomization will be used for determination of baseline data. Only patients who meet the protocol criteria for confirmation of CIC and demonstrate diary and RM compliance are eligible for randomization. This eligibility determination will include:

- A review of the baseline diary entries to ensure patients have completed at least 5 of the 7 days of diary entries in each of the 2 weeks of baseline assessments
- A review of the BM frequency data to ensure < 3 SBMs in each of the 2 weeks of the baseline diary assessment period
- A review of rescue medication use to ensure patients have not used RM for more than 2 days in each baseline week

The eligibility determination based on these criteria will be programmed into the IWRS and the system will report out eligibility (the PI or site staff will not be responsible for evaluating diary data to make the diary-based eligibility determination).

The following procedures will be performed ***only for patients eligible for randomization:***

Procedures ***prior to study drug dosing:***

- Physical examination (including body weight) and vital signs (seated blood pressure, heart rate, respiration, and body temperature)
- 12-lead ECG (semi-recumbent)
- Assess adverse events
- Safety laboratory assessments (hematology, serum chemistry, urinalysis)
- Confirm that patient is on a stable diet and has no significant changes in their consumption of liquids or fiber or their level of activity
- Blood samples for plecanatide/SP-338 concentration and immunogenicity assessments (see **Section 4.3.3** for details)
- Have the patient complete all baseline PRO questionnaires (Per Study Procedure Manual).

The first dose of study drug will be administered at the clinical site under supervision. The time of dosing will be recorded.

The following procedures will be performed ***after study drug dosing:***

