In any analysis involving abdominal bloating, abdominal discomfort, straining during a bowel movement or pain with defecation, the determination of weekly averages will follow the same methodology as described above for the abdominal pain score. That is, the weekly average item score is the sum of the non-missing scores recorded during the week, divided by the total number of non-missing scores recorded. In any week in which a patient has no non-missing item score recorded, the weekly average score will be set to missing in any summary or linear mixed-effects model analysis involving the weekly average item score.

In any analysis involving stool consistency (BSFS scores), the determination of weekly averages will follow the same methodology as presented above for abdominal pain. However, since stool consistency cannot be assessed if the patient does not have at least one SBM during the week in question (i.e., stool consistency is based on SBMs only), the weekly average will also be set to missing if no SBMs are recorded for any days in the week. Also, it is possible that a patient has no baseline weekly average stool consistency score because of the SBM criterion; in that case the patient will be excluded from any change from baseline analyses of stool consistency.

For the exploratory Responder analyses, in any given week, a patient must have at least 4 compliant diary days in that week. A compliant diary day means that the patient has responded to the BM and rescue medication use questions in the daily diary for that day. Patients who have fewer than 4 compliant diary days in a given week will be considered “non-responders” for that week. Note that this implies that for any week for which a patient has no BM or rescue medication use data, the patient is considered a non-responder; in particular, for a randomized patient who withdraws from study participation prior to the end of the study, the patient is considered a non-responder for any weeks remaining in the planned duration of the study for which the patient has no BM or rescue medication use data.

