- Enter the time of the bowel movement in 12 hour format, entering 2 digits for the hours and 2 digits for the minutes.
- For AM press 1. For PM press 2.
- Did you feel like you completely emptied your bowels during this bowel movement? If yes, press 1, if no press 0.

Please refer to the Bristol Stool Scale diagram provided by your doctor's office. Please rate the form/consistency of this stool. For Type 1, press 1, For Type 2, press 2, For Type 3, press 3, For Type 4, press 4. For Type 5, press 5. For Type 6, press 6. For Type 7, press 7.

Rescue Medication usage

- Have you taken any Dulcolax® today? If yes, press 1, if no press 0.
- How many times have you taken Dulcolax® today?
- Enter the time you took Dulcolax® in 12 hour format, entering 2 digits for the hours and 2 digits for the minutes.
- For AM press 1. For PM press 2.
- Enter the number of tablets you took

Daily Symptom Diary

The patient will be asked to rate their symptoms on a scale of 0 to 10, where 0 is NO 'ABDOMINAL PAIN' and 10 is 'ABDOMINAL PAIN' AS BAD AS YOU CAN IMAGINE.

1. Abdominal Pain. Rate your abdominal pain at its worst on a scale of 0 to 10, where 0 is NO PAIN and 10 is PAIN AS BAD AS YOU CAN IMAGINE.
2. Abdominal Bloating. Rate your abdominal bloating at its worst on a scale of 0 to 10, where 0 is NO ABDOMINAL BLOATING and 10 is ABDOMINAL BLOATING AS BAD AS YOU CAN IMAGINE.
3. Abdominal Discomfort. Rate your abdominal discomfort at its worst on a scale of 0 to 10, where 0 is NO ABDOMINAL DISCOMFORT and 10 is ABDOMINAL PAIN AS BAD AS YOU CAN IMAGINE.
4. If you had one or more bowel movement today, rate your straining with a bowel movement at its worst on a scale of 0 to 10, where 0 is NO STRAINING WITH A BOWEL MOVEMENT and 10 is STRAIN WITH A BOWEL MOVEMENT AS BAD AS YOU CAN IMAGINE.
5. If you had one or more bowel movement today, rate your pain with defecation at its worst on a scale of 0 to 10, where 0 is NO PAIN WITH DEFECATION / WITH A BOWEL MOVEMENT and 10 is PAIN WITH DEFECATION / WITH A BOWEL MOVEMENT AS BAD AS YOU CAN IMAGINE

E. PATIENT QUESTIONNAIRES

Patient Assessment of Constipation -Quality of Life (PAC-QOL), Patient Assessment of Constipation -Symptoms (PAC-SYM), Patient Global Assessment (PGA) Questionnaires

PGA will be administered electronically via IWRS, while PAC-QOL and PAC-SYM are paper-based.

PAC-QOL © PATIENT ASSESSMENT OF CONSTIPATION						

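### The baseline stool-consistency formula needs two weekly averages, so a patient with SBMs in only one baseline week has no baseline value despite usable scores

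*Combined protocol and SAP*

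**What the plan says.** Section 8.4.3 introduces the derivation with "Baseline stool consistency, severity of straining during a BM, and abdominal symptoms will be calculated as follows". It averages the non-missing scores within each baseline week and concludes that "the baseline is then equal to one-half of the sum of the two weekly average scores". It gives no alternative for a patient with only one weekly average.

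Section 8.4.1 bases BSFS on SBMs only and states that "the weekly average will also be set to missing if no SBMs are recorded for any days in the week". It foresees one consequence, that "it is possible that a patient has no baseline weekly average stool consistency score because of the SBM criterion", and excludes such a patient from change-from-baseline analyses of stool consistency.

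Eligibility limits SBMs from above only. Criterion 19 of Section 3.2 excludes patients with three or more "SBM per week for either week of the 2-week baseline diary assessment", and Section 5.2.2 requires fewer than three "SBMs in each of the 2 weeks of the baseline diary assessment period". Neither sets a lower limit.

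Two other diary items in Appendix D are conditional on a bowel movement that day: "If you had one or more bowel movement today, rate your straining with a bowel movement at its worst" and "If you had one or more bowel movement today, rate your pain with defecation at its worst".

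**The concern.** A fixed half-sum has a value only when both weeks are scored. In a population selected for infrequent SBMs, an empty week is plausible. A bowel movement within 24 hours after laxative use is not an SBM, rescue use on up to 2 days per baseline week is tolerated, and 5 of 7 diary days are enough for eligibility.

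BSFS change is listed in the synopsis as a key secondary endpoint. In the mixed model of Section 8.8.2.1 its baseline is both the reference value and a covariate, so a patient without a baseline contributes nothing. Section 8.3 bases efficacy analyses on all randomized patients, about 30 per arm. The patients lost would be those whose 1 or 2 SBMs in 14 days all fell in one week. The cost is precision, plus some shift of the analysed set towards patients with more frequent SBMs.

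**Working it through.** **Do the rules leave a gap?** An eligible patient has 0, 1 or 2 SBMs in each baseline week, which gives 3 × 3 = 9 count patterns:

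- Both weeks at least 1 SBM (4 patterns): the formula works.
- Exactly one week at 0 (4 patterns: 0+1, 0+2, 1+0, 2+0): one weekly average is missing, so the half-sum has no value.
- Both weeks at 0 (1 pattern): no score exists, and Section 8.4.1 excludes the patient.

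These are patterns, not probabilities. Example: one week has no SBM and the other averages BSFS 2.0. The formula gives ½ × (missing + 2.0) = no value. The available week gives 2.0. Counting the missing week as zero would give 1.0, the bottom of the 1-7 scale.

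The result also depends on timing. Two SBMs split 1+1 give a baseline; two SBMs split 2+0 do not.

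**How large is it?** The plan has no figure to reproduce. Let p be the chance that a baseline week has no SBM and r the correlation of that event between the two weeks. Both are assumptions.

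- Exactly one scored week: 2p(1−p)(1−r)
- Neither week scored: p² + r·p(1−p)
- Analysable per arm, as written: 30 × (1 − one − neither)
- Analysable per arm, available-week rule: 30 × (1 − neither)
- Standard-error ratio from sample size alone: √(n available ÷ n as written)

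For p = 0.20 and r = 0.3: one = 2 × 0.20 × 0.80 × 0.7 = 0.224; neither = 0.04 + 0.3 × 0.16 = 0.088; as written 30 × 0.688 = 20.6; available-week 30 × 0.912 = 27.4; ratio √(27.36 ÷ 20.64) = 1.151.

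| p, r | One week | Neither | One week, of 120 | n per arm, as written | n per arm, available-week | SE ratio |
|---|---|---|---|---|---|---|
| 0.05, 0.6 | 0.038 | 0.031 | 4.6 | 27.9 | 29.1 | 1.020 |
| 0.10, 0.6 | 0.072 | 0.064 | 8.6 | 25.9 | 28.1 | 1.041 |
| 0.10, 0.3 | 0.126 | 0.037 | 15.1 | 25.1 | 28.9 | 1.073 |
| 0.20, 0.6 | 0.128 | 0.136 | 15.4 | 22.1 | 25.9 | 1.083 |
| 0.20, 0.3 | 0.224 | 0.088 | 26.9 | 20.6 | 27.4 | 1.151 |

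This grid is not an upper limit. With independent weeks (r = 0) the one-week share is 2p(1−p): 9.5% at p = 0.05 (about 11 of 120), 32% at p = 0.20 (about 38) and 50% at p = 0.50 (60).

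**Does a noisier one-week baseline cancel the gain?** The Section 8.8.2.1 model was simulated with four arms of 30, eight weekly values, REML, a random intercept, and fixed effects for gender, treatment, week and baseline, at 1,500 runs per setting. Assumed inputs were patient SD 0.9, stool SD 0.7 to 1.5, 1 to 2 stools per scored week, follow-up slope 0.5, intercept SD 0.7, weekly residual SD 0.8, and 10% to 20% of on-treatment weeks missing.

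| p, r | Model-based SE ratio | Empirical SD ratio |
|---|---|---|
| 0.05, 0.6 | 1.020 | 1.015-1.026 |
| 0.10, 0.6 | 1.040-1.042 | 1.038-1.049 |
| 0.10, 0.3 | 1.072-1.074 | 1.059-1.075 |
| 0.20, 0.6 | 1.082-1.084 | 1.082-1.100 |
| 0.20, 0.3 | 1.152-1.154 | 1.146-1.158 |

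These ratios already include the extra noise of a one-week baseline, and they match the sample-size calculation. With a true difference of 0, the mean arm difference was −0.005 to 0.010 under both rules.

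**Other items.** Straining is named in Section 8.4.3 and is asked only on bowel-movement days, so it has the same gap. Pain with defecation is also asked only on those days and is a change-from-baseline endpoint in Section 8.8.3, but Section 8.4.3 does not name it. Gaps should be rarer for both, because any bowel movement counts.

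**The case against.** The strongest reply is that Section 8.4.1 already foresees a missing baseline and prescribes exclusion. If its sentence means no computable baseline, the plan has a complete rule and the point becomes a preference for a more inclusive one. If it means that neither week has an average, the one-week patient stays in, no precision is lost, and only a derivation detail is missing. Section 8 also promises an SAP before database lock and unblinding, where such details normally go.

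Both readings are open, and that is part of the problem. Under the first, usable scores are discarded; under the second, no formula applies. The pending SAP is the right place for the repair, but it does not alter the formula now stated.

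Several limits stand:

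- The size is wholly assumed, and the simulation's model-based ratios largely restate the sample-size calculation.
- The study is exploratory, with no testing hierarchy and no multiplicity adjustment.
- Selection is by timing as well as frequency, and the proposed rule still loses patients with no SBM in either week.
- Section 8.8.3.1 refers to all five symptom items loosely as abdominal symptom scores, so Section 8.4.3 may be meant to cover pain with defecation. Because it lists straining separately, naming this item too would remove the doubt.

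**Conclusion.** The concern holds. Applied literally, Sections 8.4.1 and 8.4.3 give no stool-consistency baseline to an eligible patient with SBMs in exactly one baseline week. Under the assumed 5% to 20% of empty weeks and correlation 0.6 to 0.3, the loss relative to an available-week rule runs from negligible (standard error 2% larger) to material for arms of 30 (15% larger). If Section 8.4.1 is instead read as keeping the one-week patient, nobody is lost, but the baseline is undefined.

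Baseline precedes randomization, so no between-arm bias is expected, and the primary endpoint does not use BSFS. The change should be made because it is cheap and improves a key secondary analysis; the trial's main conclusion does not depend on it.

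**What to change.** In Section 8.4.3, and in the SAP still to be written, define baseline as the mean of the available weekly averages: both weeks when both are scored, otherwise the one scored week. Exclude from change-from-baseline analyses only patients with neither week scored, and align the exclusion sentence in Section 8.4.1 with this. Apply the same rule to straining and pain with defecation, and name the latter in Section 8.4.3. Report by arm how many patients have two, one or no scored baseline weeks.

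The cost is one sentence and one table row, with no new data. Patients with two scored weeks keep the same value. The downside is a slightly noisier baseline for one-week patients. Section 8 lets the SAP supersede the protocol on non-primary analyses, so the rule can be fixed there before unblinding.

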8.5 DISPOSITION OF PATIENTS

Patient disposition and reasons for discontinuation from the Treatment Period of the study will be summarized by treatment group for all randomized patients.

8.6 TREATMENT COMPLIANCE

Dosing compliance will be defined by the dosing compliance ratio: the number of doses actually taken by the patient divided by the number of doses that were expected to be taken during the same period multiplied by 100. Treatment compliance is defined as taking equal to or greater than 80% of the drug dosage prescribed. Otherwise, the patient will be considered noncompliant with study treatment. Rates of treatment compliance as defined above will be compared between treatment groups using the Chi-square test.

Patient compliance with making daily electronic diary entries is monitored by the IWRS system; patients non-compliant in making daily diary entries will be withdrawn from the study.

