3.3.1 Permitted Concomitant Medications

Rescue Medication (RM) – Dulcolax®

Dulcolax® 5 mg tablets will be dispensed to patients at Visit 1, and re-supplied at the study visits as needed. From Visit 1 and for the duration of the trial, only protocol supplied Dulcolax® is to be used as the “rescue medication” (laxative) - no other laxatives are allowed. As per Dulcolax® package insert (directions for use), Dulcolax® “may be taken 1 to 2 tablets as a single dose per day”.

Patients are instructed to take rescue medication only if it has been at least 72 hours since their last bowel movement. A patient is therefore expected to have no more than two days of RM use in any given week.

Rescue medication usage will be recorded daily via the electronic diary. Sites will review rescue medication use with patients during their study visits and have the option to discontinue participation of patients who do not adhere to rescue medication guidelines.

Patients are advised NOT to take rescue medication for the period from 24 hours before to 72 hours after Day 1 of dosing. This avoids confounding the data collected in the first week of study drug administration and allows for accurate determination of the time to first BM.

Dulcolax® will be distributed to sites by Sharp Corporation. Sites may order additional bulk supplies of rescue medication by submitting a Dulcolax® Request Form. Supplies of Dulcolax® will not be reconciled at the completion of the study. Sites must track inventory of rescue medication supplies for the purpose of ensuring adequate quantities for re-supplying patients as needed. The site’s supply of rescue medication will not be managed nor automatically re-supplied.

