5.2.3 Visit 3: Week 4, Day 28 (± 3 days) of Treatment Period

The following will be completed at Visit 3:

- Collect/record unused study drug from the supply dispensed at the previous visit
- Review the electronic diary compliance reports and re-emphasize the need for diary compliance, as necessary
- Have the patient complete the PRO questionnaires (per Study Procedure Manual)

- Assess/record changes in concomitant medications and diet
- Physical examination (including body weight) and vital signs (seated blood pressure, heart rate, respiration, and body temperature)
- Safety laboratory assessments (hematology, serum chemistry, urinalysis)
- Collect blood samples for immunogenicity assessments
- Urine pregnancy test, if applicable
- Assess adverse events
- Dispense 4-week supply of study drug
- Distribute additional rescue medication (Dulcolax® tablets), if needed

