5.2.6 Early Withdrawal Visit (EW)

Patients are free to withdraw from participation in the study at any time. Investigators may choose to discontinue a patient's participation in the study if they believe it is in the patient's best interest clinically. If a patient's post-randomization compliance is of concern, contact the medical monitor to discuss. If the patient has an intervening illness that requires discontinuation of study participation, the patient and Investigator will follow procedures for early withdrawal. The following are examples of AEs that qualify for Early Withdrawal (EW):

- A positive pregnancy test will require discontinuation from the study (see **Section 7.7**).
- Changes in laboratory values, PE findings, or other assessments considered by the Investigator (or designee) to be clinically significant will require discontinuation from the study.
- Clinically significant TEAEs, including clinically significant laboratory test abnormalities or SAEs regardless of relatedness to study treatment that cause the patient, investigator, or Sponsor to feel it is not in the patient's best interest to continue.

A patient may also be withdrawn from study drug/study by the Sponsor, regulatory authorities, or the institutional review board (IRB). Patients will also be withdrawn if the entire study is terminated prematurely as described in **Section 9.10**.

Patients who discontinue early from the study should, if possible, have an Early Withdrawal Visit. The Investigator must make every effort (with proper documentation) to have the patient complete this final visit. This visit should take place as soon as possible (and within 5 days) after the patient stops taking study drug.

The following procedures will be performed at the Early Withdrawal Visit:

- Collect/record unused study drug from the supply dispensed at the previous visit
- Review the electronic diary compliance reports and re-emphasize the need for diary compliance, as necessary
- Have the patient complete the PRO questionnaires (see Study Procedure Manual)
- Assess/record changes in concomitant medications and diet
- Physical examination (including body weight) and vital signs (seated blood pressure, heart rate, respiration, and body temperature)
- 12-lead ECG (semi-recumbent)
- Safety laboratory assessments (hematology, serum chemistry, urinalysis)
- Perform urine pregnancy test, if applicable
- Collect blood samples for plecanatide/SP-338 and immunogenicity assessments

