6.6 COMPLIANCE

Patients will be advised as to how to take their daily medication and will return all unused study drug to the clinical site at each visit during the Treatment Period. The number of remaining tablets will be counted and entered into the appropriate eCRF page for that patient. Patients unwilling or unable to maintain compliance with study drug administration or procedures may be discontinued from the study at the discretion of the investigator in conjunction with the medical monitor.

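### Section 8.6 makes withdrawal mandatory for diary non-compliance, against Sections 5.2.6, 6.6 and 8.4.1, and so stops collection of outcome data that could still be obtained

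*Combined protocol and SAP*

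**What the plan says.** The passages that bear on incomplete diaries after randomisation are these.

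- **Section 8.6**, after noting that the IWRS monitors diary compliance: "patients non-compliant in making daily diary entries will be withdrawn from the study". No number of missed days is given.
- **Section 5.2.6**: "If a patient's post-randomization compliance is of concern, contact the medical monitor to discuss". Nothing here is automatic.
- **Section 6.6**: patients who do not keep up with study drug or procedures "may be discontinued from the study at the discretion of the investigator in conjunction with the medical monitor".
- **Section 5.2.3 (Visit 3)**, repeated for Visit 4: "Review the electronic diary compliance reports and re-emphasize the need for diary compliance, as necessary". Table 2 footnote g adds daily reminders and retraining where needed.
- **Section 3.2, criterion 17**, the numeric rule on diary entry: "Completion of < 5 of the 7 required daily diary entries in each week of the 2-week baseline diary assessment". Sections 4.2.1 and 5.2.2 restate it. It applies to the two baseline weeks only.
- **Section 8.4.1**: in a partly recorded week, SBMs that were entered are kept and missing days count as 0. A week with no bowel movement response is set to 0, including the weeks after withdrawal. Symptom and stool-consistency averages are left missing instead. For the exploratory responder analyses, "a patient must have at least 4 compliant diary days in that week"; a week below that is a non-response for that week alone.
- **Section 8.3**: the per-protocol population takes ITT patients who complete 8 weeks, or who stop treatment for adverse events or lack of efficacy, less major violators.
- **Section 5.2.6** also states that withdrawn patients are not replaced.

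**The concern.** A site with a patient who keeps missing diary days has three incompatible directions: withdraw (8.6), use discretion with the medical monitor (5.2.6, 6.6), or retrain and carry on (Visits 3 and 4, footnote g). Section 8.4.1 is built on the last of these, since its rules for partly complete weeks presuppose that such patients remain in the study.

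If Section 8.6 is followed, outcome data that could have been collected are not. The primary endpoint in Section 8.8.1 needs more than 3 SBMs in each of the last two treatment weeks. A patient withdrawn before Week 7, with no later diary entries, has 0 in both and is a non-responder whatever the drug was doing. The same zeros enter the mixed model for weekly SBM rate in Section 8.8.1.1. Stool-consistency and symptom scores are lost for the remaining weeks.

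The per-protocol analysis does not help. A diary withdrawal is neither a completion nor a stop for adverse events or lack of efficacy. The patient is therefore zero-filled in the ITT analysis and absent from the planned sensitivity analysis.

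**Working it through.** **1. The plan's own figure.** Section 8.2 gives mean changes of 1.2 (SD 2.6) on placebo and 3.1 (SD 4.0) on plecanatide, so the difference is 3.1 − 1.2 = 1.90. A Welch t-test at two-sided 0.05, with noncentral t and Satterthwaite degrees of freedom, has power 0.795 at 50 per group and 0.803 at 51. The stated 51 per group reproduces. At the planned 30 per group the same test has power 0.571.

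**2. Effect on the mean difference.** Assumptions not in the documents:

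- a share w of each arm is diary non-compliant;
- the problem covers a fraction f of the 8 weeks (f = 0.5 means from the end of Week 4);
- diary entry stops at withdrawal;
- baseline b is 1.5 SBMs/week (entry requires fewer than 3);
- SBMs are spread evenly over days.

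Let q be the fraction of days recorded in the affected weeks: q = 0 if withdrawn, q = 4/7 if kept with 4 of 7 days. Zero-filling as in Section 8.4.1 gives

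arm mean = μ − w·f·(1 − q)·(b + μ)

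difference = 1.90 × [1 − w·f·(1 − q)]

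With equal w in both arms, b cancels from the difference.

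Withdrawn, w = 0.10: active 3.1 − 0.10 × 0.5 × 4.6 = 2.87; placebo 1.2 − 0.10 × 0.5 × 2.7 = 1.065; difference 1.805.

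Withdrawn, w = 0.20: 2.64 − 0.93 = 1.71.

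Kept at 4 of 7 days: 1.90 − w × 0.5 × 1.90 × 3/7 = 1.859 at w = 0.10 and 1.819 at w = 0.20.

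| w per arm (f = 0.5) | Withdrawn | Kept, 4 of 7 days | Net gain | Power at n = 30: withdrawn / kept |
|---|---|---|---|---|
| 10% | 1.81 | 1.86 | 0.05 | 0.548 / 0.567 |
| 20% | 1.71 | 1.82 | 0.11 | 0.528 / 0.564 |

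Across w of 5–20%, f of 0.5 or 1.0 and b of 1.0–2.0:

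- withdrawal: difference 1.52–1.85, power 0.385–0.561;
- kept at 4 of 7 days: difference 1.74–1.88, power 0.535–0.569;
- kept at 3 of 7 days: difference 1.68–1.87, power 0.506–0.568.

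These powers are for a comparison of mean change, not for the responder proportion.

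**3. Effect on the responder endpoint.** A withdrawn patient as above has response probability 0. A retained patient does not automatically respond, because missing days still count as 0.

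- The average active patient has 1.5 + 3.1 = 4.6 SBMs/week; 4.6 × 4/7 = 2.6, which is not above 3.
- If each SBM is recorded independently, 5 true SBMs/week with 5 of 7 days gives P(at least 4 recorded) = 5(5/7)⁴(2/7) + (5/7)⁵ = 0.558 per week, and 0.558² = 0.31 for both weeks.
- For 7 true SBMs/week with 4 of 7 days, the weekly probability is 0.653 and 0.653² = 0.43.

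Retention recovers part of the loss on this endpoint, and all of it only where diary entry returns to normal by Weeks 7 and 8.

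**4. Unequal withdrawal.** If 10 percentage points more were withdrawn on active than on placebo at the end of Week 4, the active mean would fall by a further 0.10 × 0.5 × 4.6 = 0.23 SBMs/week (0.21–0.26 for b of 1.0–2.0). This is conditional arithmetic; nothing in the documents shows such an imbalance.

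**The case against.** The best defence is that the operational text is workable. The IWRS monitors diary compliance, reminders are planned, the visits call for re-education, and both 5.2.6 and 6.6 involve the medical monitor. Sites may in practice never apply the Section 8.6 sentence literally. Neither 5.2.6 nor 6.6 names the diary. This has some force, but diary entry is a study procedure, so both sections cover it, and a sentence that is not meant to be followed should not stand in the protocol.

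It is also fair that much of the damage comes from the zero-fill in Section 8.4.1, which remains after the change. That is why the comparator above is a retained patient with a sparse diary, not a fully observed one.

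Four stronger readings are tempting and are not supported.

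- **That Section 8.6 removes a patient entering 4 or 5 days a week.** It sets no threshold, so this cannot be said. The 4-day rule belongs to the exploratory responder analyses and the 5-day rule to baseline.
- **That the whole loss against complete data is recoverable.** Of the 0.095 or 0.19 SBMs/week lost, about 3/7 (43%) remains if the patient stays with 4 of 7 days recorded.
- **That withdrawals will differ by arm and bias the comparison in a known direction.** This is possible, but the documents neither show it nor give any non-compliance rate.
- **That the rescue-medication option in Section 3.3.1 is part of the same contradiction.** There sites "have the option to discontinue participation of patients who do not adhere to rescue medication guidelines". That is an option concerning rescue use, not the diary. It is a clinical-management matter, it does not conflict with 8.6, and no change to it is proposed here.

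**Conclusion.** The contradiction is plain on the page, and the passages need to be reconciled. Applied as written, Section 8.6 turns partly observed weeks into uncollected ones. For SBM and CSBM rates these become forced zeros; for symptom and stool-consistency scores they become missing values. Weeks before withdrawal are kept, and the patient stays in the ITT population.

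The size is modest and illustrative. At 10–20% non-compliance per arm from the end of Week 4, retention with 4 of 7 days recorded is worth about 0.05–0.11 SBMs/week on a difference of 1.90, with a partial gain on the responder endpoint. This rests on the Section 8.2 adult means, assumed non-compliance rates, evenly spread SBMs, and a diary that stops at withdrawal. Section 5.2.6 places the End of Study assessments two weeks after the last dose; if the diary ran until then, somewhat fewer weeks would be lost.

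The per-protocol consequence follows Section 8.3. The synopsis describes that set more loosely, as ITT patients without significant violations, and Section 8.3 leaves the detailed criteria to the SAP.

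The change is worth making because it is cheap and removes an avoidable source of missing data in a trial with 30 patients per arm and no replacement.

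**What to change.** Delete the mandatory withdrawal clause in Section 8.6. State once, with cross-references from 5.2.6 and 6.6, that incomplete diary entry after randomisation does not by itself end study participation or data collection. In its place:

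- use the reminders and retraining already planned in Section 4.2.1 and Table 2 footnote g;
- continue diary collection through Week 10;
- record diary non-compliance as a protocol deviation, against a definition written in the SAP, for the per-protocol decision before unblinding.

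Withdrawal for safety or by the patient's choice is unchanged. This concerns data collection only and proposes no rule on when study drug should be stopped.

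The cost is a wording change in an amendment, plus continued site follow-up of some patients with sparse diaries, which Section 8.4.1 already handles. No sample size figure changes.
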